1.4.2.1 Pharmacokinetics

Preliminary plasma pharmacokinetics (PK) results are available from lymphoma, solid tumor, and AML patients enrolled in Studies C34001 and C34002. In addition, preliminary urine PK results are available from lymphoma and solid tumor patients enrolled in the dose escalation cohorts of Study C34001. TAK-659 is characterized by fast absorption (overall median T_{max} [time of first occurrence of C_{max} (maximum observed concentration)] of 2 hours) in patients with hematologic and nonhematologic malignancies. Moderate variability is observed among dose-normalized steady-state AUC_{τ} (area under the plasma concentration-time curve during the dosing interval) values in lymphoma, solid tumor, and AML patients (coefficient of variation of 20.0%, 43.5%, and 34.8%, respectively). An approximately dose-proportional increase in steady state AUC_{τ} was observed over the 60 to 160 mg range in patients with AML. Mean accumulation ratios ranging from 1.90-fold to 2.54-fold and mean peak-to-trough ratios ranging from 4.34 to 5.09 were observed across the study populations after repeated QD dosing for 15 days. Based on data in lymphoma and solid tumor patients, renal clearance accounted for about 30% of TAK-659 apparent clearance, and therefore at least about 30% of TAK-659 systemic clearance. Active tubular secretion appeared to be the predominant component of renal clearance, based on comparison of unbound renal clearance to glomerular filtration rate. Geometric mean terminal disposition half-life of 34.4 hours was determined in a single dose PK run-in phase of the indolent NHL expansion cohort of Study C34001. Additional details on TAK-659 PK are provided in the TAK-659 IB.

A preliminary population PK model simulated results predicted 44% vs 30% of pts (N=2000) exposed to 80 mg BID vs 160 mg QD, respectively, would have a steady-state trough concentration of >100 ng/mL, a level leading to >90% pFLT-3 inhibition per (plasma inhibitory activity for Flt3mutant cell line in vitro) PIA(23, 24); thus forming the basis for evaluating the BID dose schedule.

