5.2 Phase Ib Dose Escalation

Dose escalation will involve only Ixazomib, increasing from 2.3 mg and then to 3 mg. Patients in each cohort will continue to the completion of the second cycle, and undergo evaluation of toxicity/tolerability prior to consideration of dose-escalation to the next cohort. The maximal dose of Ixazomib at 4mg was determined as in aforementioned myeloma studies.

Dose Cohort	Number of patients	TAK-659 (PO) Days 1-15	Ixazomib (PO) Days 1, 8, 15
1	3-6	100 mg, once daily	2.3 mg
2	3-6	100 mg, once daily	3 mg
3	3-6	100 mg, once daily	4 mg

Patients within each cohort will be followed for toxicity occurring within the first 2 cycles prior to initiating a dose/schedule escalation of the individual drugs in the next cohort, in context of the type of dose limiting toxicity (DLT) observed and to what study drug(s) the toxicity is related.

In cohort 1, If 1/3 patients develop grade ≥ 3 DLT toxicity, then 3 more patients will be entered at this dosing level; if $< 2/6$ patients develop DLT, then the next cohort will involve escalation of Ixazomib in dose.

If, on the other hand, toxicity attributable to the combination is seen in the first cohort at ≥ 2 patients, then we will consider modification of the protocol to reduce the initial dose of TAK-659 and/or Ixazomib. Again, our prior experience involving the addition of pharmacodynamically-active dosing as starting to a combination of Sorafenib and Vorinostat suggest we will not see this reduction as necessary. The dose modification plan will be based on the nature of the DLT:

Dose Cohort	Number of patients	TAK-659* (PO) Days 1-15	Ixazomib* (PO) Days 1, 8, 15
1	3-6	100 mg, once daily	2.3 mg
Dose modification plan			
		80 mg, once daily	2.3 mg Contact sponsor-investigator for consideration of schedule below 2.3mg.

*On clinic days for PK determination, TAK-659 will be taken first and then Ixazomib.

In cohort 2, if 1/3 patients develop grade ≥ 3 DLT toxicity, then 3 more patients will be entered at this dosing level; if < 2/6 patients develop DLT, then the next cohort will involve escalation of Ixazomib in dose.

Dose Cohort	Number of patients	TAK-659* (PO) Days 1-15	Ixazomib* (PO) Days 1, 8, 15
2	3-6	100 mg, once daily	3 mg
Dose modification plan based on the nature of DLT			
If DLT at least possibly related to TAK-659 OR not related to Ixazomib			
		80 mg, once daily	3 mg
If DLT at least possibly related to Ixazomib OR not related to TAK-659			
		100 mg, once daily	2.3 mg

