Patients requiring prophylaxis with fluconazole or patients whom develop active fungal infection, where isovuconazole would be appropriate, continuation of TAK-659 in the combination will require dose reduction to 60mg po daily of the TKI, and careful analysis of toxicity parameters, especially including QTc and hepatic and pancreatic enzymes. Dosing of Ixazomib will not require modification in the absence of relatable toxicity. The above determined TAK-659 dose cannot be escalated. If toxicity supervenes, the patient will be taken off study for alternative anti-infective therapy as needed. Should no toxicity be observed in a cohort, stepwise dose escalation, first to 80mg, may be considered based on review of concurrent PK measurements of specific antifungal impact on TAK-659 levels.

[figure not shown]

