6.1 Dose Delays/Dose Modifications

All toxicities that occur during the study will be actively managed following the standard of care unless otherwise specified in the protocol.

Patients who have the TAK-659 dose held due to treatment-related or possibly related AEs may resume study drug after resolution of the AE but may either maintain the same dose level or have doses of TAK-659 reduced (dose reduction) by at least 1 dose level. When a dose reduction occurs, the TAK-659 dose will be reduced to the next lower dose that either been established as a safe dose during dose escalation or is lower by a 20-mg increment. If initial dose adjustment does not provide sufficient relief, the dose of TAK- 659 can be further reduced if the treating physician considers that the patient is benefiting from study treatment and may benefit at a further reduced dose of TAK-659. When a dose reduction of TAK-659 is required due to toxicity, no dose re-escalation will be permitted.

If TAK-659 dosing is delayed for > 21 days for TAK-659-related or possibly related toxicities despite supportive treatment per standard clinical practice or more than 2 dose reductions are required in a patient, this patient should be considered to have study treatment discontinued, unless the treating physician considers that the patient may benefit from continued study treatment after resolution of AEs

to \leq Grade 1, or baseline, or a level considered acceptable by the physician. The patient will continue to be followed for 30 days for safety evaluation after the last administration of TAK-659.

Patients who experience a DLT (during escalation) or DLT-like toxicity (during phase 2 of the study) during the first cycle will, in general, require that treatment with TAK-659 be permanently discontinued. If, in the opinion of the investigator it is in the patient's best interest to continue treatment with TAK-659, then the dose of TAK-659 will be reduced by at least 1 dose level when treatment resumes after recovery of the toxicity or toxicities in question to \leq Grade 1 or to baseline values or to a level considered acceptable by the investigator. However, if a patient requires a dose delay of > 21 days for such an event to resolve despite the best supportive care permissible per protocol, then the patient must be discontinued from the study.

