13.4 Populations for Analysis

The populations used for analysis will include the following:

- **Safety population:** Patients who receive at least 1 dose of TAK-659 and Ixazomib will be used for all safety and analyses.
- **Pharmacokinetic population:** Patients who have at least one measurable post TAK-659 dose concentration.
- **Pharmacodynamics population:** Patients with sufficient dosing in Cycle 1 and sufficient pharmacodynamics data will be used for PD analyses.
- **Response-evaluable population:** Patients who receive at least 1 dose of study drugs, have measurable disease at baseline, and 1 postbaseline disease assessment will be used for analyses of response.
- **DLT-evaluable population:** the DLT-evaluable population is defined as all patients in the phase I portion of the study who either experience DLT during Cycle 1 or complete at least 75% of the planned doses of TAK-659 and Ixazomib within 2 cycles and have sufficient follow-up data to allow the investigators and sponsor to determine whether DLT occurred.

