13.8 Exploratory Objectives and Pharmacokinetic Analysis

The data analyses for these exploratory objectives are mainly descriptive. We will begin such analyses by tabulating the pairwise combinations of class1/class2 mutations that occur within the Flt3- mutant vs. -wild type cohorts and summarize the frequency of these mutations (most frequent class 1 are Flt3mutation (both ITD and TKD) ~40%; vs. N/KRAS 20%); within class 2 (NPM1 40%, IDH2/IDH1 ~20%, TET2 ~15%, WT1 ~10%, ASXL1 15%). CR/CRp vs PR/nonresponse rates will be tabulated among groups based on presence of combinational number (combinational burden) and type, and will be compared by Fisher's exact test. ORR will be summarized with 95%CI and PFS will be analyzed by Kaplan-Meier methods in the whole study population and in the subgroups defined by the mutation subtypes. Additionally, we will explore the noted response groups based on identified markers from our prior trial that were predictive of ability to achieve or not remission, including ID1, JUN, HOXA, as well as the currently added markers- β -catenin and FOXM1, examining their individual association with remission status using logistic regression model.

The plasma concentrations of TAK-659 will be determined by validated liquid chromatography tandem mass spectrometry (LC/MS/MS) assay methods. The pharmacokinetic population will be those patients whom have at least one measurable post TAK-659 dose concentration. Plasma TAK-659 concentrations will be summarized by time postdose, grouped by dosing schedule, dose group, and dosing cycle and day. Mean and individual plasma TAK-659 concentration data will be plotted over time, grouped by dosing schedule, dose group, and dosing cycle and day.

Sparse Plasma PK data from Phase I and Phase II will be used for the estimation of PK parameters in the PK-Evaluable Population, as noted in the prior section. Dose proportionality of TAK-659 plasma exposures will be evaluated by visual inspection of plots of individual PK parameter values versus dose. If data permits, regression analysis using a power model will also be used to assess dose proportionality.

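### TAK-659 dose is nearly fixed by design and, at 60 mg, confounded with CYP3A-inhibiting antifungals, so the unadjusted dose-proportionality analysis in section 13.8 is likely biased downward and otherwise imprecise

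*Combined protocol and SAP*

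**What the plan says.** Section 13.8 sets out the analysis: "Dose proportionality of TAK-659 plasma exposures will be evaluated by visual inspection of plots of individual PK parameter values versus dose". It adds: "If data permits, regression analysis using a power model will also be used to assess dose proportionality". It does not say whether dose means the assigned or the taken dose. Concentration summaries are grouped by schedule, dose group, cycle and day. Antifungal use appears nowhere in the section. The pharmacokinetic population in section 13.4 is equally open: "Patients who have at least one measurable post TAK-659 dose concentration".

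TAK-659 doses arise as follows.

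- Section 5.2: "Dose escalation will involve only Ixazomib". The cohort table gives TAK-659 100 mg once daily in cohorts 1, 2 and 3.
- Section 5.2.1, for patients needing fluconazole or isovuconazole: "continuation of TAK-659 in the combination will require dose reduction to 60mg po daily of the TKI". Exclusion criterion 15(b) in section 3.2 and section 6.3.1 also tie 60 mg to these agents.
- The section 5.2 modification tables include 80 mg after DLTs. Section 6.2 lists 80 mg and 60 mg as dose levels -1 and -2 for individual reductions. Section 6.1 adds: "When a dose reduction of TAK-659 is required due to toxicity, no dose re-escalation will be permitted".
- Phase II uses the RP2D (section 5.6), which need not be 100 mg.

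On prior evidence, section 1.4.2.1 reports for AML patients over 60 to 160 mg: "An approximately dose-proportional increase in steady state" AUC. Section 1.4.3.1 says that no drug interaction study has been done in humans.

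**The concern.** A dose-proportionality slope is interpretable only if patients at different doses are alike in whatever else determines exposure per mg. Here the dose is not varied on purpose. One of the rules that produces 60 mg does so because a drug expected to slow TAK-659 clearance is being given with it. Exposure per mg is then raised in the low-dose group by the reason for the low dose, which flattens the slope. Toxicity reductions may act in the same direction if patients with high exposure are the ones reduced, but the documents give no figure for that.

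At stake is a misleading pharmacokinetic statement: an apparent departure from proportionality that seems to contradict the earlier AML data but reflects the antifungal rule. Dose-group concentration summaries at 60 mg would also mix patients with and without an inhibitor. Section 5.2.1 makes a later step to 80 mg on an antifungal depend on a review of the antifungal's effect on TAK-659 levels, yet section 13.8 specifies no summary that isolates that effect.

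**Working it through.** The plan states no slope, precision or sample size for this analysis, so there is no figure to reproduce.

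**Inputs from the documents.** TAK-659 100 mg in the three planned cohorts (5.2). 60 mg with fluconazole or isovuconazole (3.2, 5.2.1, 6.3.1). Renal clearance about 30% of apparent clearance, hence at least about 30% of systemic clearance (1.4.2.1). CYP3A4/5 share of CYP metabolism 69.1% to 73.0% in vitro (1.4.3.1). CV of dose-normalised steady-state AUC in AML 34.8% (1.4.2.1). At most 54 patients (synopsis).

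**Assumptions.** R is the exposure ratio with versus without the antifungal at the same dose. f is the share of 60 mg patients taking one. b is the true exponent.

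**Expected slope.** With ln(exposure) = a + b·ln(dose), 100 mg patients uninhibited and the rest at 60 mg:

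expected slope = b − f·ln(R)/ln(100/60), where ln(100/60) = 0.511.

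Example: b = 1, f = 1, R = 1.33 gives 1 − 0.285/0.511 = 0.44.

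| R (b = 1) | f = 1 | f = 0.5 | f = 0.25 |
|---|---|---|---|
| 1.0 | 1.00 | 1.00 | 1.00 |
| 1.1 | 0.81 | 0.91 | 0.95 |
| 1.25 | 0.56 | 0.78 | 0.89 |
| 1.33 | 0.44 | 0.72 | 0.86 |
| 1.5 | 0.21 | 0.60 | 0.80 |
| 1.67 | 0.00 | 0.50 | 0.75 |

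At R = 1.67 the cut from 100 to 60 mg exactly offsets the inhibition, so the two groups have equal exposure.

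**What R might be.** If all non-renal clearance were CYP metabolism, the CYP3A fraction would be 0.70 × 0.691 = 0.484 to 0.70 × 0.730 = 0.511. With a proportion i of CYP3A clearance inhibited, R = 1/(1 − fraction × i): 1.14 to 1.15 at i = 25%, 1.32 to 1.34 at 50%, 1.63 to 1.69 at 80%. The fraction is near a ceiling. If renal clearance were 50%, R at i = 50% would be 1.21 to 1.22. The inhibited proportion is not in the documents.

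**Precision.** SD of log exposure = √ln(1 + 0.348²) = 0.338, and the SE of the slope = 0.338/√Sxx. These are illustrative mixes of 54 patients with one value each.

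- 44 at 100 mg and 10 at 60 mg: Sxx = (44 × 10/54) × 0.511² = 2.13, SE 0.23.
- 38/6/10 at 100/80/60 mg, all ten on an antifungal: expected slope 0.48 at R = 1.33 and 0.06 at R = 1.67, SE 0.23. With five of the ten on one: 0.74 and 0.53.
- No antifungal-exposed samples, 48 at 100 mg and 6 at 80 mg: Sxx = (48 × 6/54) × ln(100/80)² = 0.27, SE 0.66.
- No antifungal-exposed samples, 44/6/4 at 100/80/60 mg: SE 0.32.
- Everyone at 100 mg: Sxx = 0 and no slope can be estimated.

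In the 38/6/10 mix with all ten exposed and R = 1.33, the bias of 0.52 exceeds two standard errors. Without exposed samples this bias is gone, but the slope is weakly determined.

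**The case against.** The strongest reply is that little depends on this. Dose proportionality is not among the objectives or endpoints in section 2. The section 13.8 analyses are mainly descriptive, the main method is a plot, and the regression is conditional on the data. The PK criterion in section 5.3 uses concentration limits, not a slope. All of that stands and sets the priority.

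Four stronger readings are tempting, and the documents do not support them.

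- That every 60 mg patient is on an antifungal. Section 6.2 also gives 60 mg as a toxicity reduction, and 80 mg can arise by cohort modification or as the RP2D. Patients newly enrolled at such a dose are not selected for their own exposure.
- That the slope falls far below 1 whatever the true pharmacokinetics. The bias depends on R and f, and the fitted slope also on b. There is no antifungal bias at R = 1 or f = 0. With b = 1.3, f = 0.5 and R = 1.33 the slope is 1.02, so the confounding could instead hide a true exponent above 1.
- That the regression uses the dose taken. The text says only dose. Reading it as assigned dose does not rescue the analysis, because the three planned cohorts then have no contrast.
- That exposure-response plots are distorted. Exposure raised by an inhibitor is still the patient's exposure, and no mechanism for distortion is shown.

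Section 13.8 does foresee a separate population PK plan, which could handle inhibitor use, but it is optional and does not govern the analysis described here.

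**Conclusion.** The point holds, at low priority. TAK-659 dose is nearly constant by design and, at 60 mg, confounded with moderate CYP3A inhibition. With no adjustment in section 13.8, the expected slope is pulled below the true exponent for any R above 1 whenever some 60 mg patients take the antifungal. For a true exponent of 1, R between 1.1 and 1.67 puts it between 0.81 and 0 if all 60 mg patients are exposed, and between 0.91 and 0.50 if half are. These figures rest on assumed R and f, since the documents give neither. Selection through toxicity reductions may add to the bias but is not quantified. Removing the antifungal bias leaves an estimate with an SE of roughly 0.3 to 0.7 in the illustrative mixes, or none at all if only 100 mg remains.

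**What to change.** In section 13.8:

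1. Define dose as the TAK-659 dose actually taken at the time of the sample.
2. In the dose-proportionality plot and power model, exclude samples taken with fluconazole or isovuconazole, or include antifungal use as a covariate. If every 60 mg patient is exposed and all exposed samples are at 60 mg, the covariate absorbs those samples and the two options give the same slope.
3. Flag samples taken after an individual toxicity-driven reduction and run a sensitivity analysis without them.
4. Summarise concentrations by dose and antifungal use.
5. If only one dose remains, omit the dose-proportionality assessment and leave it to the pooled population PK analysis, with CYP3A-inhibitor use as a covariate.

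The cost is SAP wording and one flag derived from concomitant-medication records that sections 5.7 and 8.1 already require. The downside is fewer samples and a wide interval in an exploratory analysis. No dosing rule needs to change.

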13.9 Biomarker Analysis

As noted above, the relationship between observed clinical response and candidate biomarkers will be explored to identify a biomarker(s) predictive of sensitivity and/or resistance to TAK-659/Ixazomib. Developing the potential predictive biomarker(s) of TAK-659/Ixazomib mediated antitumor activity may require analysis of data from multiple patients.

PD changes from baseline will be tabulated and summarized by patient, dose, and patient genotype, including Flt3 status and accompanying epigenetic mutations. Additionally, the relationship between changes in the PD marker and TAK-659 plasma exposure may be explored graphically and the PK/PD relationships may be explored using mathematical models as appropriate and permitted by the data. The relationship between changes in the PD marker and clinical response will also be explored.

13.10 Safety Analysis

Safety evaluations will be based on the incidence, intensity, and type of AEs; and clinically significant changes in the patient's vital signs, weight, and clinical laboratory results. Safety variables will be tabulated and presented for the safety population. Exposure to study drug and reasons for discontinuation of study treatment will be tabulated.

Treatment-emergent AEs that occur after administration of the first dose of study drug and through 30 days after the last dose of study drug, or until the start of subsequent antineoplastic therapy, whichever occurs first, will be tabulated. Treatment-emergent events will also include any AE that is considered by the investigator to be drug-related regardless of the start date of the event, or any event that is present at baseline but worsens in intensity or is subsequently considered by the investigator to be drug related.

AEs will be tabulated according to the Medical Dictionary for Regulatory Activities (MedDRA) coding dictionary for the purpose of summarization. AEs are to be tabulated using MedDRA system organ class, high-level term, and preferred term, and will include the following categories:

- Treatment-emergent AEs
- Drug-related treatment-emergent AEs
- Grade 3 or higher treatment-emergent AEs
- Grade 3 or higher drug-related treatment-emergent AEs

The most commonly reported treatment-emergent AEs (ie, those events reported by $\geq 10\%$ of all patients in the safety population) will be tabulated by the MedDRA preferred term.

Tabulation also will be provided that enumerates AEs by maximum intensity. Deaths, SAEs, and AEs resulting in study drug discontinuation will be tabulated. Clinical laboratory parameters will be summarized at each scheduled time point. Shift tables will be produced for selected laboratory parameters. These tables will summarize the number of patients with each baseline NCI CTCAE grade and changes to the worst NCI CTCAE grade during the study.

Descriptive statistics for the actual values of vital signs and weight over time will be tabulated by scheduled time point.

All concomitant medications collected from screening through study period will be classified by preferred term according to the WHO drug dictionary.

Additional safety analyses may be determined at any time without prejudice to enumerate rates of toxicities and to further define the safety profile of study drugs.

13.10.1 Electrocardiogram

A summary of ECG abnormalities will be presented by visit. ECG intervals (QT, QTcB, QTcF, PR, QRS, and heart rate) will be summarized at each scheduled time point, along with change from baseline to each post treatment time point.

13.11 Interim Analysis

Due to the two stage designs of the phase II study, there will be a predefined decision rule at the end of the first stage to decide on whether the study regimen is active enough to move on the second stage. This is not a formal interim analysis; there will be no formal interim analysis for this study. Of note, in the phase II study, the FLT-3 mutant and FLT-3 WT cohorts will be evaluated independently and could be subject to enrollment hold without affecting the other cohort.

